3.8.3. Definition of End of Treatment

The End of Treatment value will be defined as the Week 12 value, either scheduled or windowed per Table 5. If a Week 12 value is not available, the last non-missing value on or before the last dose date will be used.

CONFIDENTIAL

4. Analysis Sets

Table 5 defines the analysis sets to be used.

Table 5 Analysis Sets

Analysis Sets	Description
Screened	All patients who sign the ICF
Randomized	All patients who are randomized into any one
	of treatment groups. Treatment assignment will
	be based on the randomized treatment.
Pharmacokinetic (PK)	All randomized patients who received at least 1
	dose of TERN-501 and/or TERN-101 and have
	evaluable PK data. Treatment assignment will
	be based on the treatment actually received.
Pharmacodynamic (PD)	All randomized patients who received at least 1
	dose of study drug (TERN-501, TERN-101,
	and/or placebo) and for whom PD markers can
	be evaluated. Treatment assignment will be
	based on the treatment actually received.
PK/PD sub-study	All randomized patients who consented to and
	participated in the PK/PD sub-study and
	received at least 1 dose of study drug (TERN-
	501 and/or TERN-101). Treatment assignment
	will be based on the treatment actually
	received.
Safety	All randomized patients who received at least 1
	dose of study drug. Treatment assignment will
	be based on the treatment actually received.
Efficacy	All randomized patients who received at least 1
	dose of study drug. Treatment assignment will
	be based on the randomized treatment.
Per Protocol (PP)	All randomized patients who have completed
	the study without any major protocol deviations
	affecting the interpretation of the efficacy, PK,
	or PD results

CONFIDENTIAL

5. Examination of Subgroups

Subgroups will be assessed at Baseline and only if there are a sufficient number of patients in each group, i.e., at least 5 patients in each treatment group. Each efficacy analysis description in Section 7 includes the description of subgroup analyses.

Baseline subgroups of interest are as follows:

- Age categories: $< 65, \ge 65$ years
- Sex: Male, Female
- Baseline BMI: $< 30 \text{ kg/m}^2, \ge 30 < 35 \text{ kg/m}^2, \ge 35 < 40 \text{ kg/m}^2, \ge 40 \text{ kg/m}^2$
- Baseline Comorbidity of diabetes (yes, no) will be based on Medical History case report form, Medical Dictionary of Regulatory Activities (MedDRA) preferred term Baseline use of Statins defined by the WHODD Standardized Drug Grouping (SDG) of 'Statins'. This subgroup will only be used for the safety analysis of lipids (Section 8.3.3).
- cT1 classified as elevated (800 875 msec) and high (>875 msec)

CONFIDENTIAL

6. Study Population

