9.3. Analysis Sets

The following analysis sets are defined:

Analysis Sets	Description
Screened	All patients who sign the ICF
Randomized	All patients who are randomized into any one of treatment groups. Treatment assignment will be based on the randomized treatment.
Pharmacokinetic (PK)	All randomized patients who received at least 1 dose of TERN-501 and/or TERN-101 and have evaluable PK data. Treatment assignment will be based on the treatment actually received.
Pharmacodynamic (PD)	All randomized patients who received at least 1 dose of study drug (TERN-501, TERN-101, or placebo) and for whom PD markers can be evaluated. Treatment assignment will be based on the treatment actually received.
PK/PD sub-study	All patients who consented to and participated in the PK/PD sub-study and received at least 1 dose of study drug (TERN-501, TERN-101, or placebo). Treatment assignment will be based on the treatment actually received.
Safety	All patients who received at least 1 dose of study drug. Treatment assignment will be based on the treatment actually received.
Efficacy	All randomized patients who received at least 1 dose of study drug. Treatment assignment will be based on the randomized treatment.

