2.1. Overall Study Design

This study is a multicenter, randomized, double-blind, placebo-controlled, parallel-group treatment, phase 2a study.

Approximately 140 non-cirrhotic NASH patients with fibrosis identified based on prior liver biopsy and/or imaging and clinical criteria who meet study eligibility criteria will be enrolled and randomized equally into 7 groups: once daily orally administered TERN-501 1 mg (n=20), TERN-501 3 mg (n=20), TERN-501 6 mg (n=20), TERN-501 10 mg (n=20), TERN-101 10 mg (n=20), or matching placebo (n=20).

Of the 140 patients randomized, approximately 42 patients (approximately 6 per group) will take part in an intensive PK and pharmacodynamic (PD) collection after the first dose and after the last dose of study drug. Patients who are not participating in the PK/PD sub-study will have sparse PK and trough PD sampling only.

The total study duration will be approximately 22 weeks, consisting of a 6-week Screening Period, a 12-week Treatment Period, and a 4-week Follow-up Period.

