2.1.3. Study Drug

Study drug is defined as any investigational intervention(s), marketed product(s), or placebo intended to be administered to a study patient according to the study protocol.

Final, Version 2.0, 26JULY2023

CONFIDENTIAL

Statistical Analysis Plan CONFIDENTIAL Labcorp Drug Development Study: 000000231152 Protocol Reference: TERNCB-2002

Table 1 Study Drug

Intervention Name	TERN-501 capsules	Placebo to match (identical in shape, size, appearance, and color to TERN-		TERN-101 Placebo to match (identical in shape, size, appearance, and color to TERN-
Type	Dena	501 capsules)	Drug	101 tablets)
Type Dose	Drug Capsule	Drug Capsule	Tablet	Drug Tablet
Formulation Section	Capsule	Capsule	Tablet	Tablet
Unit Dose Strength(s)	1 mg or 3 mg per capsule	N/A	5 mg per tablet	N/A
Route of Administration	Oral	Oral	Oral	Oral
Use	Experimental	Placebo	Experimental	Placebo
IMP and NIMP	IMP	IMP	IMP	IMP
Sourcing	Provided centrally by the Sponsor	Provided centrally by the Sponsor	Provided centrally by the Sponsor	Provided centrally by the Sponsor
Packaging and Labeling	Study drug will be provided in a labelled carton containing one/two bottles of capsules for 4-week use. Each bottle and carton will be labeled as required per country requirements.	Study drug will be provided in a labelled carton containing one/two bottles of capsules for 4-week use. Each bottle and carton will be labeled as required per country requirements.	Study drug will be provided in a labelled carton containing one/two bottles of tablets for 4-week use. Each bottle and carton will be labeled as required per country requirements.	Study drug will be provided in a labelled carton containing one/two bottles of tablets for 4-week use. Each bottle and carton will be labeled as required per country requirements.

Patients will be instructed to take one capsule/tablet from each bottle by mouth daily, at approximately the same time each day, on an empty stomach (no food or drink besides clear liquids for approximately 2 hours before and 1 hour after study drug administration), for a total of 2 capsules and 2 tablets each day as shown in Table 6.

Protocol Reference: TERNCB-2002

CONFIDENTIAL

For subjects participating in the PK/PD sub-study, study drug should be administered approximately 24 hours prior to their Week 12 visit.

Table 2 Study Drug Administration by Dose Group

Dose Group	TERN-501 Capsules	TERN-501 Placebo to	TERN-101 Tablets	TERN-101 Placebo to
	Capsules	Match	Tablets	Match

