7.18.3. PK/PD Analyses

For patients in the PK/PD substudy, Day 1 and Week 12 PK and PD (7α C4 and FGF19) concentrations will be plotted together by treatment group over time. Similarly, AUCs, C_{min} , and C_{max} for PK and PD will also be plotted by treatment group.

Final, Version 2.0, 26JULY2023

CONFIDENTIAL

8. Safety Analyses

All safety analyses will be conducted using the safety analysis set unless otherwise noted.

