8.5. Electrocardiograms

Summary statistics will be provided for heart rate, PR interval, QRS interval, QT interval, and QTcF at each visit. The investigator interpretation is collected as normal, abnormal not clinically significant (NCS), or abnormal clinically significant (CS). Patients whose interpretation shifts from normal to abnormal (CS or NCS) will be listed separately including description of the abnormality and any associated comments.

Categorical summaries will for baseline, worst post-baseline, and change from baseline for the following QTcF values will be presented:

- > 450 msec
- > 480 msec
- > 500 msec
- Change from baseline > 30 msec
- Change from baseline > 60 msec

CONFIDENTIAL

All ECG results will be presented in by-patient data listings. If applicable, cardiologist consult information will be presented in a separate by-patient data listing.

CONFIDENTIAL

9. Other Assessments

Other assessments will be provided in by-patient data listings only; no summary tables will be provided, including but not limited to the following:

- Eligibility details including unmet eligibility criteria
- Informed consent
- Randomization schema
- Physical examination collection information
- Serology
- Pregnancy testing
- FSH test
- Urine drug screen
- Alcohol test
- Urinalysis and Urine Microscopic Examination
- Coagulation
- Hemoglobin A1c
- Direct bilirubin
- Indirect bilirubin
- Laboratory reference ranges
- Cardiology consult
- Overdose
- Comments

Final, Version 2.0, 26JULY2023

CONFIDENTIAL

10. Changes to Protocol Planned Analyses

There were no changes from the protocol planned analyses.

CONFIDENTIAL

Statistical Analysis Plan CONFIDENTIAL Labcorp Drug Development Study: 000000231152 Protocol Reference: TERNCB-2002

11. Appendices

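### The SAP's PK/PD sub-study set omits the placebo patients whom the protocol includes, and the SAP does not declare the change.

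*SAP*

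**What the plan says.** Protocol 9.3 defines the PK/PD sub-study set as "All patients who consented to and participated in the PK/PD sub-study and received at least 1 dose of study drug (TERN-501, TERN-101, or placebo", so placebo is in. SAP Section 4, Table 5 gives the corresponding definition but narrows the drugs to "501 and/or TERN-101). Treatment assignment", so placebo is out. SAP Section 10 states: "There were no changes from the protocol planned analyses".

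Other parts of the SAP point towards including placebo:

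- SAP 2.1.3: "Study drug is defined as any investigational intervention(s), marketed product(s), or placebo".
- SAP 2.1 plans intensive sampling in "approximately 42 patients (approximately 6 per group", over seven groups of which one is placebo.
- The Pharmacodynamic set in the same Table 5 names placebo explicitly: "and/or placebo) and for whom PD markers can".

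The analyses refer to their populations by several labels. SAP 7.17 uses a *PK Sub-study Analysis Set*, which Table 5 does not define. SAP 7.18 restricts the PD parameters to *PD patients*. SAP 7.18.2 names no set. SAP 7.18.3 begins "For patients in the PK/PD substudy, Day 1 and Week 12 PK and PD".

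**The concern.** Intensive 7αC4 and FGF19 sampling is done only in the sub-study (Protocol 1.3 and Appendix 2). Outside it, 7αC4 is a trough measurement and FGF19 is scheduled only at early termination. The placebo patients in the sub-study are therefore the only source of placebo within-day profiles.

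Those profiles matter for interpretation. Protocol 5.3.2 has sub-study patients fast until 2 hours after the dose and then lets them eat, so the 4-hour and 6-hour samples can follow a meal. In the earlier TERN-101 phase 2a study, FGF19 peaked at 6 hours (Protocol 2.2.2.2). Actively treated patients have a pre-dose sample on Day 1 but no drug-free profile over the day. A display without placebo cannot separate the effect of drug from the effect of food and time of day.

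The definition also has a reporting consequence. SAP 6.1 requires the number of patients in each analysis set, the number randomized to the sub-study, and a listing of reasons for exclusion from each set. A wrong definition feeds directly into all but the second of these.

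**Working it through.** **Inputs.** Seven groups with about 6 sub-study patients each (SAP 2.1; Protocol 4.1); about 140 randomized (same sections); the two set definitions (Protocol 9.3; SAP Table 5); the pairwise comparisons (SAP Table 6).

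**1. The planned size.** 7 groups × 6 = 42. This reproduces the stated figure, and only if placebo is one of the groups.

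**2. The SAP definition read literally.** 6 active groups × 6 = 36. The loss is 42 − 36 = 6 patients, and 6/42 = 14%. All of them are placebo.

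**3. Effect on SAP 6.1.** The denominator there is the number randomized. The set would be reported as 36/140 = 25.7% instead of 42/140 = 30.0%. The same summary gives the number randomized to the sub-study, about 42, so the two lines would disagree. The listing would show every placebo sub-study patient as excluded from a set in which the protocol places them.

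**4. Effect on each analysis that might use the set.**

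- *PK parameters (SAP 7.17).* Nothing is lost. Placebo samples are not assayed for drug (Protocol 6.4; SAP 2.1.4), and the PK set is limited to active drug in both documents.
- *PD parameters and ANOVA (SAP 7.18 and 7.18.2).* The parent section restricts these to PD patients. The nearest Table 5 entry is the Pharmacodynamic set, which includes placebo. SAP 7.18.2 reports pairwise differences between groups. Table 6 has 8 comparisons: 6 active groups against placebo, and 2 combinations against TERN-501 alone. If that scheme applies, 6 of the 8 could not be run without placebo. The natural reading keeps the control.
- *PK/PD plots (SAP 7.18.3).* The text refers to patients in the sub-study and does not say whether this means participation or the Table 5 set. Under the first meaning the placebo 7αC4 and FGF19 curves appear. Under the second they do not.

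**The case against.** The strongest objection is that this is a drafting slip with no analytic effect. SAP 2.1.3 already defines study drug to include placebo. The PD parameters follow the PD set. The pairwise scheme presupposes a placebo group. No PD analysis invokes the Table 5 sub-study set by its exact name, and the wording in 7.18.3 can be read as describing participation. For PK, leaving placebo out is correct.

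Most of this stands. A reader might infer from Table 5 that the SAP removes the placebo control from the formal 7αC4 and FGF19 analysis. The documents do not support that, for the reasons in step 4 above.

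Two things remain. First, the general definition of study drug does not rescue the set. The parenthesis in Table 5 is specific, and the Pharmacodynamic row of the same table lists placebo where it is wanted, so a programmer could take the omission as deliberate. Second, the labels are loose enough that the safe reading has to be inferred. *PD patients* and *PK Sub-study Analysis Set* are not Table 5 names, and the wording in 7.18.3 closely resembles the name of the set that omits placebo. The SAP 6.1 count and listing depend on the definition itself, so the benign reading of Section 7.18 does not repair them.

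**Conclusion.** The set definition is wrong as written, at minor severity. SAP Table 5 departs from Protocol 9.3, conflicts with the SAP's own definition of study drug and sub-study plan, and is not declared in SAP Section 10.

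Taken literally, it excludes about 6 of about 42 patients and misstates the set in SAP 6.1. It puts the placebo PD curves in the 7.18.3 plots at risk, but only if those plots are programmed from the Table 5 set. It would be too strong to say that the plan removes the control from the intensive PD profiles: the 7.18.2 comparisons most naturally retain it.

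The counts assume that enrolment follows the plan of about 6 per group. The conclusion about 7.18.2 assumes that PD patients means the Pharmacodynamic set. 7αC4 and FGF19 are exploratory, and no primary or secondary endpoint is touched.

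**What to change.** - In SAP Table 5, restore the protocol's list for the PK/PD sub-study set: TERN-501, TERN-101, or placebo.
- In SAP 7.18 and 7.18.2, state that PD patients means the PD analysis set, which for these parameters is the sub-study patients with intensive samples, placebo included.
- In SAP 7.18.3, state that the PD displays include placebo.
- Exclude placebo only from the PK concentration and parameter outputs.

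With the first change the set returns to about 42, and SAP Section 10 needs no entry on this point. The cost is a few words in Table 5 and a sentence or two in 7.18. No new data, sampling or change of model is needed.

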6.1. Patient Disposition

Patient disposition will be summarized for the Screening Analysis Set by treatment group and overall total. The summary will include:

- Number of patients screened.
- Number of screen failures, i.e., screened but not randomized, with reasons for screen failure. The denominator for percentage of screen failures will be the number of patients screened. The denominator for percentages for reasons for screen failures will be the number of screen failures.
- Number randomized. The denominator for percentage of randomized patients will be the number of patients screened.
- Number randomized and not treated. The denominator for percentage of randomized and not treated patients will be the number of patients randomized.
- Number in each analysis set. The denominator for percentage in each analysis set will be the number of randomized patients. In addition, the number of patients randomized to the PK/PD substudy will be presented.
- Number who discontinued treatment early and reason(s) for discontinuation of treatment. The denominator for percentages will be the number of randomized and treated patients (Efficacy Analysis Set).
- Number who discontinued from study prior to completing the study and reason(s) for discontinuation. The denominator for percentages will be the number of randomized and treated patients (Efficacy Analysis Set).

A by-patient data listing of study disposition information including the reasons for treatment and/or study termination will be presented. Withdrawal of consent details will also be included, if applicable.

A by-patient data listing including the reasons for exclusion from each analysis set will be presented.

6.2. Demographics and Baseline Characteristics

Demographic variables will include the following:

- Age at informed consent including the subgroup of < 65 years vs ≥ 65 years
- Sex
- Race
- Ethnicity

CONFIDENTIAL

Other baseline characteristics will include the following:

- Weight (kg)
- Height (cm)
- BMI (kg/m²) including the following subgroups:

$$\circ$$
 < 30,

$$\circ \ge 30 - < 35$$

$$\circ \geq 35 - < 40$$

$$\circ \geq 40 \text{ kg/m}^2$$

- Baseline liver stiffness measure (LSM) by transient elastography (kPa)
- Baseline Controlled Attenuation Parameter (CAP; dB/m)
- Baseline LFC (%) by MRI-PDFF
- Baseline cTI (msec) by MRI including the following subgroups:

$$\circ$$
 Elevated (800 – 875 msec),

$$\circ$$
 and High (> 875 msec).

- Liver Biopsy within 1 years of randomization
 - Baseline fibrosis stage (F1, F2, F3)
 - Baseline NAFLD Activity Score (NAS)
- Baseline ELF including the following subgroups:

• Low
$$(< 7.7)$$

- Intermediate ($\geq 7.7 \text{ to } < 9.8$)
- High (≥ 9.8)
- Baseline PRO-C3 including the following subgroups:
 - < 17.5

CONFIDENTIAL

- ≥ 17.5
- Baseline FAST Score including the following subgroups:
 - < 0.67
 - ≥ 0.67
- Baseline Comorbidities will be based on Medical History case report form, Medical Dictionary of Regulatory Activities (MedDRA) preferred term (PT)
 - O Diabetes status (yes, no) will be defined as PT preferred term (PT) includes "diabetes mellitus" or "Diabetic neuropathy" will be assigned yes, otherwise no.
 - o Hypertension (yes, no) will be defined as PT of "Hypertension" will be assigned yes, otherwise no.
 - O Dyslipidemia (yes, no) will be defined as Standardized MedDRA query (SMQ) of "Dyslipidemia (SMQ)" will be assigned yes, otherwise no.
 - Primary hypothyroidism (yes, no) will be defined as Standardized MedDRA
 Hypothyroidism (SMQ)
- Baseline medication use, defined as starting prior to first administration of study drug, regardless of end date:
 - Statins defined by the WHODD Standardized Drug Grouping (SDG) of "Statins"
 - PCSK9 inhibitors defined by the WHODD terms "Inclisiran", "Alirocumab",
 "Evolocumab"
 - Fish oil defined by the WHODD Standardized Drug Grouping (SDG) of "Omega-3 Fatty Acid"
 - Fibrates defined by the WHODD Standardized Drug Grouping (SDG) of "Fibrates"
 - Levothyroxine defined by the WHODD Standardized Drug Grouping (SDG) of Levothyroxine
 - Antihypertension medications defined by the WHODD SDG of "Antihypertensives"

CONFIDENTIAL

- Antithrombotic medications defined by WHODD SDG of "Antithrombotic drugs"
- Antidiabetic medications defined by the WHODD SDG of "Drugs used in diabetes"
- Hormonal contraceptives defined by the WHODD SDG of "Drugs used in Hormonal contraception"
- Vitamin E defined by the WHODD drug codes beginning in "001105" or if "VITAMIN E" is found in the preferred drug name
- Pioglitazone or other PPARγ agonists defined by WHODD ATC level 4 A10BD and A10BG
- o GLP-1 analogues defined by WHODD ATC level 4 code (term) A10BJ (Glucagon-like peptide-1 [GLP-1] analogues)
- DPP-4 inhibitors defined by WHODD ATC level 4 code (term) A10BH (Dipeptidyl peptidase 4 [DPP-4] inhibitors)
- SGLT2 inhibitors defined by WHODD ATC level 4 code (term) A10BK (Sodium-glucose co-transporter 2 [SGLT2] inhibitors)

The following baseline laboratory tests will be summarized as continuous variables and as frequencies for categorizations described:

- Baseline ALT level (U/L):
 - $\circ \le 60 \text{ U/L versus} > 60 \text{ U/L (overall and by sex)}$
 - < 2x ULN versus $\ge 2x$ ULN to < 5x ULN
- Baseline AST level (U/L): The same subgroups as specified for ALT above will be used
- Baseline GGT level (U/L): $\leq ULN$, > ULN
- Baseline ALP level (U/L): $\leq ULN$, > ULN
- Baseline total bilirubin level (mg/dL)
- Baseline fasting HDL cholesterol (mg/dL)
- Baseline fasting LDL cholesterol (mg/dL)

CONFIDENTIAL

- Baseline fasting total cholesterol (mg/dL)
- Baseline fasting triglycerides (mg/dL)
- Baseline fasting glucose level (mg/dL)
- HbA1c (%): $< 6.5\%, \ge 6.5\%$
- Baseline platelet count $(10^9/L)$:
- Baseline free T3 (FT3)
- Baseline total T3
- Baseline free T4
- Baseline total T4
- Baseline TBG
- Baseline rT3
- Baseline FT3/rT3

Demographics and baseline characteristics will be summarized by treatment group and overall, for the Safety, Efficacy, and Per Protocol Analysis Sets.

All demographic and baseline characteristics data will be presented in by-patient data listings.

No inferential statistical comparisons will be performed.

6.3. Protocol Deviations

Protocol deviations will be identified and documented in the clinical trial management system (CTMS). Major protocol deviations that could potentially affect the conclusions of the study will be identified prior to database lock and unblinding of individual patient treatment information.

Major protocol deviations include, but are not limited to

- Patients who entered the study even though they did not satisfy the entry criteria.
- Patients who developed withdrawal criteria during the study but were not withdrawn.
- Patients who received the wrong treatment or were dispensed an incorrect dose.

CONFIDENTIAL

• Patients who received an excluded concomitant treatment.

All protocol deviations and major protocol deviations will be summarized separately by treatment group and overall total for each deviation category using the Efficacy Analysis Set.

All protocol deviations and separately only major protocol deviations will be presented in a by-patient data listing.

6.4. General Medical History

All medical history conditions will be coded using the Medical Dictionary of Regulatory Activities (MedDRA). Medical history will be summarized by treatment group and overall total by system organ class and preferred term, using the Safety Analysis Set. Summaries will be ordered by descending order of the overall incidence of system organ class and preferred term within each system organ class.

